1.1 Preoperative diagnosis of intrauterine adhesions

There is currently a consensus on the diagnosis and assessment of intrauterine adhesions. The gold standard is hysteroscopy ^[4]. The existing IUA severity scoring standards are all based on hysteroscopic findings. Commonly used scoring standards include the American Fertility Society (AFS) (1988) score ^[5]. The European Society of Gynecological Endoscopy (ESGE) (1998) score ^[6], the March (1978) score ^[7] and the Chinese expert consensus on the clinical diagnosis and treatment of intrauterine adhesions published in 2015 ^[8]. However, hysteroscopy is an invasive examination that depends on the surgeon's skill and subjective impression ^[6]. When the cervical canal, the lower segment of the uterine cavity, or even the uterine cavity is completely closed, hysteroscopy may fail, and the condition of the uterine cavity cannot be fully assessed. It may even cause uterine perforation. In IUA patients with reproductive tract malformations such as unicornuate uterus, it is difficult to determine the correct shape of the uterine cavity under hysteroscopy. Hysteroscopic distension fluid may cause water intoxication. Furthermore, the above limitations, such as the need for anesthesia and high cost, limit its use as a routine screening for intrauterine adhesions. Currently, a large number of studies have demonstrated that four-dimensional ultrasound has a high accuracy in diagnosing intrauterine adhesions. Correlation analysis with hysteroscopy results shows that four-dimensional ultrasound diagnosis of intrauterine adhesions is consistent with hysteroscopy results ^[6]. Studies have also confirmed that multiple ultrasound parameters can accurately screen for intrauterine adhesions ^[7]. Menstrual status, number of intrauterine procedures, uterine cavity morphology, endometrial continuity, endometrial homogeneity, endometrial-myolipin boundary, endometrial blood flow, peristaltic waves, etc. can all be used as evaluation criteria for diagnosing intrauterine adhesions ^[7-8].

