However, the characteristics of post-IUA three-dimensional ultrasound images are highly variable and easily affected by machine noise and physician diagnostic experience; how to accurately extract image features is a bottleneck in its application. The information from the four diagnostic methods of TCM is complex, and how to simplify complex information is a challenge for its use in prediction. The integration and enhancement of multidimensional TCM and Western medicine risk factors is a key challenge in establishing a post- IUA infertility risk prediction model. Machine learning technology holds promise for solving these bottlenecks.

2. Research Objectives

2.1 To reveal the intrinsic relationship between three-dimensional ultrasound image characteristics and diagnosis and prognosis in the IUA population;

2.2 Multicenter clinical studies have confirmed the clinical efficacy of the cold knife plowing technique and uterine stent in preventing adhesions;

2.3 Standardize treatment plans for renowned doctors and prescriptions to promote endometrial growth and maintain pregnancy and assist in conception, and confirm their clinical efficacy;

2.4 Construct and validate a multidimensional infertility risk factor prediction model based on integrated traditional Chinese and Western medicine after IUA, and visualize it for easy application;

3. Research Design

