3.1 Establish four-dimensional ultrasound diagnostic evaluation standards

A super-resolution model for enhancing 3D ultrasound images was trained using transfer learning across multiple tasks, and its parameters were fine-tuned to obtain a super-resolution model capable of enhancing IUA 3D ultrasound image features. Lesions in the reproductive terminal chain (ovary, follicle, uterus, endometrium, myometrium-mesenchymal junction, and fallopian tubes) were annotated on the enhanced 3D ultrasound images , resulting in a large-scale, precisely annotated IUA 3D ultrasound image dataset. Using this dataset and object detection algorithms in artificial

intelligence, automatic and accurate detection of lesions in the reproductive terminal chain can be achieved, thus enabling accurate diagnosis of IUA 3D ultrasound. Furthermore, a scoring standard was constructed based on the characteristic indicators of endometrial receptivity assessed by 4D ultrasound.

3.2 Standardize IUA diagnosis and treatment data and build a large database and data queue

To strengthen the standardization and normalization of integrated traditional Chinese and Western medicine (TCM) diagnosis and treatment, and addressing the current lack of unified standards for IUA (Intrauterine Adnexation) medical data , this project pioneered the development of the "Expert Consensus on Integrated TCM and Western Medicine Diagnosis and Treatment of IUA." This consensus standardizes preoperative diagnosis, preoperative TCM conditioning, surgical procedures, postoperative TCM treatment, and pregnancy guidance for IUA, and has been disseminated and promoted nationwide. A national-level big data platform has been established, relying on TCM clinical research bases and national regional obstetrics and gynecology medical centers. The database is constructed in two parts: based on established multi-dimensional data standards , previous IUA data (including images) is collected and cleaned, and clinical information data extraction and storage methods are improved to establish a systematic, structured, and standardized integrated TCM and Western medicine IUA big data database across multiple centers ; simultaneously, regional medical centers connect the information systems of hospitals within the network region to the medical center through the data platform, providing real-time monitoring and follow-up , and contributing to the establishment of an IUA cohort dataset.

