A super-resolution IUA ultrasound image enhancement algorithm based on transfer learning was developed. Lesions in the reproductive terminal chain (ovary, follicle, uterus, endometrium, myometrium- mesenchymal junction, and fallopian tubes) were annotated on the enhanced 3D ultrasound images. Based on the enhanced 3D ultrasound image features of the IUA reproductive terminal chain from the second part of the study, and the multimodal large dataset from the first part of the study, deep learning and natural language processing technologies were combined to achieve multimodal data feature extraction and fusion, enabling automatic detection of IUA clinical subtyping, thus constructing an AI-based IUA classification and grading algorithm. Two machine learning methods were used to construct a predictive model for post-IUA infertility risk: traditional logistic regression and XGBoost . The logistic regression model used stepwise regression to screen variables, combining the minimum Akaike information criterion, Bayesian information criterion, and clinical significance to determine the final

predictive factors included in the model. After determining the predictive factors, a predictive model was established using the logistic regression equation to predict the probability of post-IUA infertility. The effect of the predictive factors was reflected by the regression coefficient or OR value and its 95% CI. After model establishment, multicollinearity tests were performed. Multicollinearity is assessed using the correlation coefficient method/variance inflation variable. Strong collinearity among variables can severely impact the model's generalization ability. XGBoost, short for "Extreme Gradient Ascent," is an ensemble machine learning algorithm based on decision trees and using a gradient boosting framework. It employs the Boruta algorithm to select the final predictive factors for inclusion in the model. The importance of predictive factors is reflected by the SHAP (Shapley Additive Explanation) value; a higher SHAP value indicates a more important predictive factor. The resulting model combines a Logistic Regression model and an XGBoost model to predict infertility risk after IUA (Intrauterine Access) surgery.

8. Data integrity and quality assurance

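### Lesion labels for the detector are set on super-resolution images and no stated step checks them against the original scans or hysteroscopy, so agreement with them would not show lesions that the enhancement adds or erases

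*Protocol*

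**What the plan says.** Section 3.1 of the protocol sets out a sequence. A super-resolution model is trained by transfer learning and fine-tuned for 3D ultrasound of intrauterine adhesions. Lesions of the ovary, follicle, uterus, endometrium, tubes and related structures "were annotated on the enhanced 3D ultrasound images", "resulting in a large-scale, precisely annotated IUA 3D ultrasound image dataset". The next sentence begins "Using this dataset and object detection algorithms in artificial" and concludes that "automatic and accurate detection of lesions in the reproductive terminal chain can be achieved", which is then said to make accurate ultrasound diagnosis possible.

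Section 7, headed as the statistical analysis plan, restates the step ("A super-resolution IUA ultrasound image enhancement algorithm based on transfer learning was developed", followed by annotation on the enhanced images). It passes the enhanced-image features on to an AI algorithm for subtyping and grading. The summary says the same.

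Two background statements bear on this. Section 1.1 says of diagnosis: "The gold standard is hysteroscopy". Section 1.5 describes the image characteristics after treatment as "highly variable and easily affected by machine noise and physician diagnostic experience".

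**The concern.** A detector is only shown to be accurate to the extent that its reference labels are right. Here the reference is a reading of a processed image. If the processing changes what is visible, the change can reach both the detector's input and the label used to judge it, and the two will agree for the wrong reason.

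At stake are the claim of accurate detection and diagnosis in Section 3.1, the grading algorithm in Section 7, and the part of objective 2.1 that links image characteristics with diagnosis.

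**Working it through.** **Step 1: what the labels can and cannot reveal.** Consider how a detector that takes enhanced images as input would be judged against labels set on the same enhanced images.

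| Situation | Label on enhanced image | Detector result | Counted against that label as |
|---|---|---|---|
| Real lesion erased by enhancement | none | not flagged | correct negative |
| False structure added, annotator labels it | lesion | flagged | correct positive |
| False structure added, annotator declines to label it | none | flagged | false positive (error is seen) |
| Real lesion visible only after enhancement | lesion | flagged | correct positive (rightly) |

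The first two rows are errors that this comparison cannot show. The erased lesion is the clearer case, because the annotator has nothing to see. The added structure is hidden only if the annotator labels it.

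**Step 2: is there an independent check elsewhere?**

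- Section 5 plans a 7:3 random split, a prospective external set, AUC with the DeLong test, the Brier score and the Hosmer-Lemeshow test. All of these are applied to the logistic and XGBoost infertility-risk models. Neither the enhancement model nor the detector is mentioned.
- Section 1.1 names hysteroscopy as the reference for diagnosis. Nothing in Sections 3.1, 5 or 7 links hysteroscopic findings to the annotation or to the detector.
- No section provides for reading the unenhanced scans or for checking the fidelity of the enhancement.

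**Step 3: how far does it reach?** Section 7 sends the enhanced-image features to the subtyping and grading algorithm, so that algorithm is affected. Sections 3.4 and 4.3 list image features among the candidate predictors of infertility, without saying that they come from enhanced images. The outcome there is pregnancy over two years of follow-up, which does not depend on any image label. An error in those features could not hide in that AUC or calibration.

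**Step 4: size.** The document gives no detector metric, enhancement error rate or lesion prevalence by structure, so there is no figure to reproduce. The following is illustration on assumed values only.

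*Erased lesions.* Let e be the share of true lesions erased, and suppose the detector finds 95% of the lesions labelled on enhanced images and none of the erased ones. Sensitivity against all true lesions is 0.95 × (1 − e):

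- e = 5%: 0.95 × 0.95 = 0.90
- e = 10%: 0.95 × 0.90 = 0.86 (0.855)
- e = 20%: 0.95 × 0.80 = 0.76

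The figure against the enhanced-image labels stays at 0.95 throughout.

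*Added lesions.* Let f be the share of lesion-free structures in which a false lesion is added **and** labelled, p the true lesion prevalence, and suppose the detector reproduces the labels perfectly. True specificity is 1 − f, and true positive predictive value is p / (p + (1 − p) f):

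| p | f = 5% | f = 10% |
|---|---|---|
| 20% | 0.20 / 0.24 = 83% | 0.20 / 0.28 = 71% |
| 40% | 0.40 / 0.43 = 93% | 0.40 / 0.46 = 87% |

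True specificity is 95% or 90%, while both apparent figures are 100%. All participants have adhesions, so prevalence for endometrial lesions may well be higher than these values. The formula then gives a smaller loss in predictive value.

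**The case against.** The strongest reply is that the protocol describes no scoring of the detector at all. A reader might infer that enhancement errors are counted as correct in every accuracy figure. The documents do not support that: the only performance figures planned are those of the infertility-risk models, and these are judged against pregnancy outcomes. Detector metrics might also be set in a separate analysis plan that is not at hand, so their absence is not the point here. The labelling rule, however, is positively fixed in Section 3.1 and repeated in Section 7 as the basis for the accuracy claimed.

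A reader might also infer that the detector's accuracy cannot be checked. That is too strong. The original scans exist, since they are the input to the enhancement, and surgery is done under a hysteroscope. A check is feasible but not stated.

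Three further replies have force:

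- The enhancement model is fine-tuned for these images, and Section 1.5 presents noise as the problem to be solved. This may lower the risk, but it does not measure it.
- Labelling enhanced images is coherent if the detector will be used on enhanced images. That supports keeping them for input and training, not using them as the sole reference.
- Original scans are no perfect truth either. Section 1.5 says so, and a lesion made visible only by enhancement would count as a false positive against them. Hysteroscopy has limits too, which Section 1.1 sets out. This argues for reporting against more than one reference.

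**Conclusion.** The point holds in a limited form. Lesion labels are set on super-resolution images, they are the only labels named for the detector, and no stated step compares them with the original scans or with hysteroscopy. Agreement with them would not show lesions that the enhancement erases, or those that it adds and the annotator labels. The detection, diagnosis and grading claims are affected; the AUC and calibration of the infertility-risk models are not.

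The size cannot be derived from the document. The illustrative figures rest wholly on assumed error rates, prevalence and detector behaviour. They show only that the gap would be material at modest error rates, not that such rates occur. The change is worth making because the claim of accurate detection otherwise has no support independent of the enhancement.

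**What to change.** In Sections 3.1 and 7:

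- Set aside a test set split by patient. Have the same annotators label its original, unenhanced volumes without seeing the enhanced version.
- Report detector performance on this set against the original-image labels as well as against the enhanced-image labels.
- For uterine-cavity lesions on preoperative scans, also report performance against the hysteroscopic findings recorded at surgery. This assumes that such findings are captured with the surgical details listed in Section 4.3. It will not serve postoperative scans, where ultrasound replaces repeat hysteroscopy, nor the ovary, follicle and tubes. For those, the original-image reading is the available reference.
- Rest the claim of accurate detection on these enhancement-independent references. Enhanced images may stay as model input and for training labels.

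The cost is a second reading of the test images by annotators already in place and a little more analysis, with no new scans. Reported accuracy will probably be lower, and some original images will be read as indeterminate. Some lesions visible only after enhancement will count as false positives against the original reading. Showing the results against each reference side by side lets readers judge that last effect.

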Patients with intrauterine adhesions diagnosed and treated at our hospital and the branch centers of this project: aged 18-45 years; collection began after ethical review was approved, with a total of 5,000 cases collected, of which 2,000 cases were collected by our center.

Exclusion criteria:

Patients with abnormal ovarian function, male infertility, and inability to cooperate with diagnosis, treatment, and follow-up.

Statistical methods: A super-resolution IUA ultrasound image enhancement algorithm based on transfer learning was used. Lesions in the reproductive terminal chain (ovary, follicle, uterus, endometrium, myometrium- mesenchymal junction, and fallopian tubes) were annotated on the enhanced 3D ultrasound images. Based on the enhanced 3D ultrasound image features of the IUA reproductive terminal chain from the second part of the study, and the multimodal large dataset from the first part

of the study, multimodal data feature extraction and fusion were achieved using deep learning and natural language processing techniques to realize automatic detection of IUA clinical subtyping, thereby constructing an AI-based IUA classification and grading algorithm.

Research Text

1. Research Background

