The big data platform of the Traditional Chinese Medicine Clinical Research Base and the National Regional Medical Center for Obstetrics and Gynecology encompasses health data from over 50 gynecological specialty alliance units nationwide,

including Xiangya Third Hospital of Central South University, the First Affiliated Hospital of Hunan University of Traditional Chinese Medicine, Xiangya Hospital of Central South University, Xiangya Second Hospital of Central South University, Hunan Provincial Maternal and Child Health Hospital, and Hunan Provincial People's Hospital. Based on the existing IUA case database, IUA patients from the past two years were retrospectively screened. Most of these patients underwent transvaginal 3D ultrasound follow-up on days 20-24 of their menstrual cycle one month after surgery. More than 5,000 IUA patients with relatively complete information were identified, sufficient for subsequent machine learning modeling needs. Furthermore, patients within the past two years could clearly recall their disease, making the retrospective investigation and supplementary data reliable. Data was collected on individual patient information, family history, lifestyle, past medical history, marital and reproductive history, clinical symptoms, clinical diagnosis, laboratory test results, treatment methods, postoperative 3D ultrasound images, male partner fertility-related information, and TCM syndromes. (This project involves the collection and analysis of clinical medical records of IUA patients, **which has been approved by the Ethics Committee of the chair unit, Xiangya Third Hospital of Central South University, and filed with the alliance units** .) Data underwent standardization, cleaning, and outlier/ missing value handling . Simultaneously, unified follow-up standards and evaluation mechanisms were established to strengthen follow-up examinations and monitoring of the cohort population, forming a comprehensive monitoring and follow-up system. Follow-up efforts were intensified, with reproductive follow-ups conducted every 3 months, utilizing multiple channels such as WeChat, telephone, and Douyin (TikTok) to improve timeliness. Pregnancy outcomes were followed up two years after the start of conception . Multi-center clinical diagnosis and prognostic information collection was completed, constructing a multi-center IUA cohort for Chinese women.

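### Section 3.1 claims ultrasound diagnosis of IUA, but every planned dataset holds only women with IUA, so patient-level specificity cannot be estimated

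*Protocol*

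**What the plan says.** The selection criteria in the Research Proposal Summary admit "Patients with intrauterine adhesions diagnosed and treated at our hospital and the branch centers of this project: aged 18-45 years", "with a total of 5,000 cases collected, of which 2,000 cases were collected by our center". The exclusion criteria only narrow this group further.

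Section 4.1 describes the retrospective modelling data in the same terms: "More than 5,000 IUA patients with relatively complete information were identified". Section 3.1 annotates lesions on enhanced three-dimensional images, "resulting in a large-scale, precisely annotated IUA 3D ultrasound image dataset". It then applies object detection and concludes that "automatic and accurate detection of lesions in the reproductive terminal chain can be achieved, thus enabling accurate diagnosis of IUA 3D ultrasound". The heading of 3.1 speaks of diagnostic evaluation standards.

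Objective 2.1 is "To reveal the intrinsic relationship between three-dimensional ultrasound image characteristics and diagnosis and prognosis in the IUA population". Section 1.1 names hysteroscopy as the gold standard and lists drawbacks that "limit its use as a routine screening for intrauterine adhesions". It then reports that published studies found ultrasound accurate.

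The summary's statistical methods and section 7 describe a narrower use of the images: subtyping, classification and grading of IUA. Section 5 evaluates only the models for infertility risk after IUA.

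**The concern.** A diagnostic standard has to separate women who have the condition from women who do not. The women on whom such a standard can fail by over-calling are those with a suspicious scan and a clear cavity at hysteroscopy. The entry rule leaves them out, and no other section brings them in.

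If the claim stays, the final report could present the algorithm as a validated diagnostic tool with nothing known about its false-positive rate at patient level. Preoperative ultrasound diagnosis and assessment is the first step of the new management model in section 3.3, so readers may well take the claim at face value. Who is enrolled is fixed in the protocol, so a separate statistical analysis plan could not repair it.

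**Working it through.** **No figure to reproduce.** The protocol gives no sensitivity, specificity or precision for ultrasound diagnosis. The check is whether the quantities behind a diagnostic claim can be estimated at all.

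**Inputs**
- Prospective women with IUA: 5,000, of whom 2,000 are at the lead centre (summary).
- Retrospective women with IUA: more than 5,000 (section 4.1).
- Women without IUA: none planned in any section.
- Reference standard: hysteroscopy (section 1.1).

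**Patient-level accuracy, IUA versus no IUA**
- Sensitivity = TP/(TP + FN), with a denominator of up to 5,000. At an assumed sensitivity of 0.90, the 95% half-width is 1.96 × √(0.90 × 0.10/5,000) = 0.0083, about 0.8 points. With the lead centre's 2,000 it is 1.96 × √(0.90 × 0.10/2,000) = 0.0131, about 1.3 points.
- Specificity = TN/(TN + FP) = 0/0, undefined.
- The area under the ROC curve is the share of case/non-case pairs ranked correctly. The number of pairs is 5,000 × 0 = 0, so it is undefined.
- A cut-off based on sensitivity + specificity − 1 is undefined for the same reason.

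The retrospective set also has 0 non-cases, so pooling the two sets changes nothing. Nor do more cases or better images.

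**What the same data can support**
- Lesion-level or region-level detection. A mark placed on an unaffected structure in a woman with IUA is a false positive and can be counted.
- Subtyping and severity grading, because these vary between women with IUA.
- Image features against pregnancy outcome. Infertility varies within the cohort, so the discrimination and calibration measures in section 5 are sound in this respect.

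**Illustration of what stays unknown.** Assume a sensitivity of 0.90 and borrow the 22.0% in section 1.5 as if it were a prevalence. Then PPV = 0.22 × 0.90/(0.22 × 0.90 + 0.78 × FPR) = 0.198/(0.198 + 0.78 × FPR).

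| False-positive rate | PPV |
|---|---|
| 5% | 0.198/0.237 = 84% |
| 10% | 0.198/0.276 = 72% |
| 20% | 0.198/0.354 = 56% |
| 40% | 0.198/0.510 = 39% |

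The study could not tell these rows apart. The 22.0% is the share of female infertility attributed to IUA, not the prevalence among women scanned, so the table shows only how wide the uncertainty is.

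**Non-cases needed if the claim were kept.** n = 1.96² × p(1 − p)/h². For a half-width h of 5 points this gives 246, 139 or 73 hysteroscopy-negative women at an assumed specificity p of 0.80, 0.90 or 0.95. For 3 points it gives 683, 385 or 203.

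**The case against.** The strongest reply is that the specified analysis never attempts diagnosis. Section 7 and the summary promise subtyping and grading, section 5 evaluates infertility models only, and no sensitivity or specificity for IUA is announced. Section 1.1 treats ultrasound accuracy as already shown elsewhere. This stands, and it limits the point to the heading and one claim in 3.1. It does not remove it, because 3.1 still derives accurate diagnosis from this study's own image set.

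Some stronger readings are tempting but unsupported:

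- **That objective 2.1 also promises a diagnostic standard.** It names a relationship inside the IUA population. It confirms the restriction, since the presence of IUA does not vary there.
- **That an algorithm could call every uterus affected and score perfectly.** This is true of a yes/no call per woman, but not of the object detection in 3.1, where marks on unaffected structures count against it.
- **That women without adhesions would be sent to adhesion surgery.** Section 3.3 describes diagnosis and treatment together through an integrated hysteroscope, and section 4.2 leaves the surgical plan to the gynaecology department. Nothing gives the algorithm that decision. A false positive might still lead to an invasive hysteroscopy, so the harm is conditional.

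One could also argue that cavities free of adhesions after surgery might serve as negatives. No such comparison is defined. The new model replaces repeated hysteroscopy with ultrasound, so the reference test would often be missing. Treated uteri also do not represent women presenting for a first diagnosis.

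**Conclusion.** The point holds for IUA versus no IUA at patient level. The specificity denominator is 0 beside 5,000 planned cases, so the diagnostic claim in 3.1 has no support in the design. This rests on one reading: that women entered as diagnosed and treated for IUA do have it. A few misdiagnosed women might slip in, but they would not form a planned comparison group.

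The positive predictive values are illustrative and are not a measured effect of this design. A reader might infer that the imaging work as a whole fails. It does not, because detection, grading and prognosis within IUA remain estimable. The treatment comparison and the infertility models (objectives 2.2 to 2.4) are untouched by this point. It is a moderate correction to 3.1.

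**What to change.** **Recommended.** Restrict the heading and claim of 3.1 to lesion localisation, subtyping or grading, and prognosis in women with known IUA. Delete the closing clause that moves from lesion detection to accurate diagnosis. State that diagnosis in objective 2.1 means grading within IUA. This brings 3.1 into line with the summary and section 7. It costs a wording amendment and a narrower claim; enrolment and procedures do not change.

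**Optional, only if the sponsor wants to keep the diagnostic claim.** For the imaging part alone, include consecutive women with suspected IUA who have both preoperative ultrasound and hysteroscopy, keep those with a clear cavity, and report sensitivity and specificity. The centres must first confirm that such women have both examinations and that the records and images are kept; the protocol states neither. Scan-negative women who are not referred to hysteroscopy would remain unverified, so the estimates would need that caveat. The cost is an eligibility amendment for the imaging part and the handling of the extra records: about 139 hysteroscopy-negative women for ±5 points at an assumed specificity of 0.90.
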